#### **Recruitment and Screening**

Subjects will be recruited through the use of printed material, targeted solicitation through the Pennington Biomedical Center email listserv and social media. The Pennington recruiting department will screen potential subjects over the phone, and those meeting basic eligibility criteria (age, self-reported BMI, medical and medication history) will be scheduled for a screening visit.

Subject eligibility criteria will be evaluated at a single screening visit. The screening visit will occur in the outpatient clinic, in the morning following confirmation of an overnight (at least 8 hours) fast. Subjects who provide informed consent will proceed with the tests and measurements of the screening visit. Subjects who satisfy the eligibility criteria will be enrolled in a study cohort. The schedule of assessments is provided in Table 2.

### Randomization Procedure and Blinding

Each subject in the cohorts will be randomly assigned one of the relevant treatment sequences in order of enrollment. Treatment sequence assignments will be balanced so that each sequential block will have unique treatment sequences. As an example, the first three enrolled subjects in each cohort will be randomly assigned to one of three distinct treatment sequences, as will enrollees 4-6 and 7-9. As a result, three of the nine subjects in each cohort will be randomly assigned to each of the three treatment sequences. The randomization scheme will be prepared by [name] under the supervision of [name]. Except for the pharmacist who will prepare and dispense the capsules, all study staff and the investigators will be blinded to the randomization.

Table 2. Schedule of Assessments

	Screening	Visit 1a	Visit 1b	Visit 2a	Visit 2b	Visit 3a	Visit 3b
Consent	x						
Height	x						
Weight	x	x		x		x	
Blood Pressure/Pulse/Temperature	x	x		x		x	
Medical History Questionnaire	x						
Pregnancy Test (Urine)*	x						
Concomitant Medications	x						
Chemistry Panel/CBC	x						
Adverse Events		x	x	x	x	x	x
Plasma naringenin			x			x	x
Chemistry Panel/CBC (0 hr)**		x		x		x	
Chemistry Panel/CBC (24 hrs later)**			x		x		x
Naringenin Administration		x		x		x	
IV Placement		x					
Blood Collection at 0, 2, 3, 3.5, 4, 4.5, 6, 8, and 12 hours		x					

\* Women of Child bearing potential

\*\* For Cohort 2 only BUN, AST, and Bilirubin added to Chem 15 panel

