#### Visit 1 (13 hours, fasting for at least 8 hours)

To start the study, eligible subjects will arrive at the clinic in the morning following an overnight fast (except for water) that began no later than 8 hours prior to the study appointment. The following tests and measurements will be performed:

- Weight, vital signs (blood pressure, pulse, and temperature).
- Blood collection for a CBC and Chemistry 15 panel.

- Subjects will be given a 150 mg dose of naringenin or placebo, administered orally.
- Blood collection for pharmacokinetic study of 150 mg dose of naringenin at 2, 3, 3.5, 4, 4.5, 6, 8, and 12 hours.
- Subjects will be provided a meal 5 hours after naringenin administration and at the end of the pharmacokinetic testing.

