**Visit 1b (½ hour, fasting for at least 8 hours)**

- Subjects will return 24 hours post naringenin administration and blood will be drawn for CBC, Chemistry 15 panel, and to evaluate serum naringenin concentrations.
- Adverse events will be assessed 24 hours after naringenin dosing.

Subjects will return to the clinic to complete Visit 2 no less than seven days after the completion of Visit 1.

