**Visit 2a (½ hour, fasting for at least 8 hours)**

Subjects will arrive at the clinic in the morning following an overnight fast (except for water) that began no later than 8 hours prior to the study appointment. The following tests and measurements will be performed:

- Weight and vital signs (blood pressure, pulse, and temperature).
- Blood collection for a CBC and Chemistry 15 panel.
- Subjects will consume 150 mg or 300 mg dose of naringenin or placebo, administered orally.

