**Visit 2b (½ hour, fasting for at least 8 hours)**

- Subjects will return 24 hours post naringenin administration and blood will be collected for CBC, and Chemistry 15 panel.
- Adverse events will be assessed 24 hours after naringenin dosing.

Subjects will return to the clinic to complete Visit 3 no less than seven days after the completion of Visit 2.

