**Visit 3a (5 hours, fasting for at least 8 hours)**

Subjects will arrive at the clinic in the morning following an overnight fast (except for water) that began no later than 8 hours prior to the study appointment. The following tests and measurements will be performed:

- Weight and vital signs (blood pressure, pulse, and temperature).
- Blood collection for a CBC and Chemistry 15 panel
- Subjects will consume 300 mg dose of naringenin or placebo, administered orally.
- Blood collection at four hours for measurement of serum naringenin.

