**Visit 3b (½ hour, fasting for at least 8 hours)**

- Subjects will return 24 hours post naringenin administration and blood will be collected for CBC, Chemistry 15 panel, and serum naringenin concentrations.
- Adverse events will be assessed 24 hours after naringenin dosing.

The visits for Cohort 2 will be similar to Cohort 1 with the exception of oral naringenin dose to be administered (Table 1), and that BUN, AST, and Bilirubin will be added to the Chemistry 15 panel at visits 1a, 1b, 2a, 2b, 3a, and 3b.

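### No blood pressure, pulse or temperature reading is scheduled in the 24 hours after any of the 54 administrations, so the primary safety outcome has no systematic post-dose vital sign

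*Combined protocol and SAP*

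**What the plan says.** The Schedule of Assessments (Table 2) has one vital-sign row, "Blood Pressure/Pulse/Temperature", marked at Screening, 1a, 2a and 3a only. The visit descriptions agree with it:

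- **Dosing visits.** At Visit 1 the list opens with "Weight, vital signs (blood pressure, pulse, and temperature"), followed by the safety blood and then the dose. Visits 2a and 3a follow the same order. After the dose, Visit 1 lists timed pharmacokinetic bloods and meals, Visit 2a lists nothing, and Visit 3a lists "Blood collection at four hours for measurement of serum naringenin".
- **24-hour visits.** Visit 1b: "Subjects will return 24 hours post naringenin administration and blood will be drawn for CBC, Chemistry 15 panel", plus serum naringenin. Visit 2b: "Subjects will return 24 hours post naringenin administration and blood will be collected for CBC, and Chemistry 15 panel". Visit 3b: "Subjects will return 24 hours post naringenin administration and blood will be collected for CBC, Chemistry 15 panel, and serum naringenin concentrations". Each adds an adverse-event assessment. None lists a vital sign.
- **Next period.** Visit 2 takes place "no less than seven days after the completion of Visit 1", and the same minimum gap separates Visits 2 and 3. Nothing is scheduled after Visit 3b.

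Cohort 2 follows a similar schedule, with only the doses and three added analytes named as differences. Under Statistical Considerations, the primary outcome is safety and tolerability, judged on clinical as well as biochemical grounds.

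**The concern.** Vital signs and weight are the only objective clinical measures in the schedule, and neither has a post-dose value within a period. The adverse-event definition counts a clinically significant vital-sign change, including worsening from baseline, as an event. No reading is scheduled that could show such worsening soon after a dose. Adverse events are sought mainly by open-ended questions, which cannot detect a change the subject does not feel.

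If the plan is followed exactly, a table with no vital-sign adverse events would say little about blood pressure, pulse or temperature at any dose. That table would feed the Cohort 1 safety summary, which is reviewed before the 600 mg and 900 mg cohort begins. This is a gap in the schedule. It does not contradict the adverse-event definition.

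**Working it through.** **Inputs.** Table 1: six sequences, three subjects each, three dosing visits. Table 2 and the visit lists: timing of assessments. Rationale for Naringenin Dose: half-life 2.31 ± 0.4 h.

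**1. Administrations.** 3 subjects × 3 sequences × 2 cohorts = 18, which reproduces the stated sample size. 18 × 3 visits = 54 administrations: 9 at each of four doses = 36 active, and 18 placebo.

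**2. Scheduled vital signs.** 18 × 4 = 72 readings: 18 at screening and 54 on dosing days, listed before the dose. Readings at 1b, 2b and 3b: 18 × 0 = 0. Chemistry/CBC and adverse-event assessments at those visits: 18 × 3 = 54 of each.

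**3. Time to the next scheduled reading.**

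| Given at | Administrations | Next scheduled vital sign |
|---|---|---|
| Visits 1 and 2 | 36 | next period's arrival, at least 7 days later (about 8 if the visit is complete only at its b part) |
| Visit 3 | 18 (12 active in Sequences 1, 3, 4, 6; 6 placebo in Sequences 2, 5) | none |

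**4. What added readings would give.** At 24 h: 54 of 54 administrations, with 9 within-subject placebo comparisons per dose. At the existing 4-hour draws of Visits 1a and 3a: 12 + 12 = 24 active and 6 + 6 = 12 placebo, 36 in all. That is 6 of the 9 subjects at each dose and 12 of 18 on placebo. The other 18 administrations (12 active, 6 placebo) fall at Visit 2, where subjects stay half an hour.

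**5. What each time point can support.** In each cohort the numbers of subjects at Visits 1/2/3 are: lower dose 6/3/0, higher dose 0/3/6, placebo 3/3/3. Dose and period are therefore entangled. For a least-squares model per cohort with subject and treatment effects, and s² the within-subject variance (not given in the documents, so only ratios are used), the variance of a dose-minus-placebo contrast is:

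- 24 h, no period effect: s²(1/9 + 1/9) = 2/9 s² = 0.222 s².
- 24 h, with period: 4/15 s² = 0.267 s²; residual df = 27 − 9 − 2 − 2 = 14. Adjusting for period raises the variance by (4/15)/(2/9) − 1 = 20%.
- 4 h, Visits 1a and 3a only, with period: 4/3 s² = 1.333 s²; residual df = 18 − 9 − 2 − 1 = 6. This is (4/3)/(4/15) = 5 times the 24-hour variance.

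At 4 h each dose has only 3 direct within-subject placebo contrasts, all from one sequence (150 mg: Sequence 2; 300 mg: Sequence 3; 600 mg: Sequence 5; 900 mg: Sequence 6). Each is fully confounded with period. The adjusted estimate exists only by borrowing across sequences, so the 4-hour data are descriptive.

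**6. Distance from exposure.** 24/2.31 = 10.4 half-lives; range 24/2.71 = 8.9 to 24/1.91 = 12.6. A 24-hour reading alone may miss a transient effect.

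**The case against.** The strongest reply is that the plan never names vital signs as a primary measure. Its safety section specifies chemistry and CBC at 0 and 24 hours, and its safety analysis counts adverse events by treatment against placebo. Both are collected after all 54 administrations, and Table 2 also marks adverse events on the dosing days. Clinical assessment could be read as that questioning. The protocol also says its staff take vital signs under site standards of practice, promises ongoing monitoring by the investigators, and lets clinical findings trigger a safety review. It reports no adverse events in six volunteers at 135 mg or in 18 subjects given a single 1000 mg dose with a bioavailability enhancer, and it excludes people with cardiovascular disease or chronic medication.

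Part of this stands. The primary outcome does have systematic post-dose data, and the gap is confined to vital signs. The background bears on how likely an effect is. Unscheduled readings are possible, and the site standards cannot be seen from here. But none of these provisions schedules a measurement, and questioning cannot find a symptomless change.

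Two further points are fair. First, pre-dose timing is inferred. Table 2 gives no clock time, the lists are not strictly chronological (Visit 1 lists the 5-hour meal after the 12-hour blood), and only the time 0 blood is expressly placed before the dose. If post-dose readings were intended, the text would still need correcting, and there would be no same-visit baseline. Second, the remedy is limited: its formal comparison is at 24 hours, well after exposure, and the 4-hour reading is descriptive and missing for Visit 2. A period-adjusted model with nine subjects per dose is also modest evidence, in a trial with no power basis. These limits should be stated in the plan. They do not make having no scheduled reading preferable.

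**Conclusion.** The concern holds. Table 2 and all six visit descriptions agree, and no other section schedules a post-dose reading: 0 of 54 administrations have a vital sign scheduled in the following 24 hours, and the 18 at Visit 3 have none afterwards at all. The conclusion rests on reading the dosing-day vital signs as pre-dose, which the list order supports but no text states. It concerns what the plan makes systematic. It does not claim that staff would never take an unscheduled reading, or that the trial is invalid. The change should be made: it closes a real gap in the primary outcome at little cost.

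**What to change.** In Table 2 and the Visit 1 to Visit 3b descriptions, for both cohorts:

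1. Label the blood pressure, pulse and temperature readings at 1a, 2a and 3a as pre-dose.
2. Add the same readings at 1b, 2b and 3b.
3. Add a reading in all subjects at the 4-hour blood draws of Visits 1a and 3a.

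In the safety analysis, summarise change from the same visit's pre-dose value by treatment. Compare the 24-hour change with placebo within subject, with period in the model. Report the 4-hour change descriptively only. State the limits: 24 hours is about 10 half-lives after dosing, and the 18 Visit 2 administrations would have no reading near exposure. Treating 4 hours as near exposure is an assumption, because the documents give no peak time.

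The cost is a few minutes of staff time per reading and some wording. No extra visit, blood, equipment or visit length is needed: subjects already return at 24 hours, and are already on site for 13 hours at Visit 1 and 5 hours at Visit 3a.

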### CLINIC VISITS

Subject in each cohort will complete one screening visit and three study visits.

#### Screening Visit (1½ hours)

Subjects will report to Pennington Biomedical in the morning following an overnight fast (except for water) that began no later than 8 hours prior to the study appointment. The screening visit includes explanation of the study purpose, procedures, and signing of the informed consent. If the participant agrees to participate by signing a consent form, the following tests and measurements will be performed:

- Self-report of personal and family medical history.
- Height, weight, vital signs (blood pressure, pulse, and temperature).
- Concomitant medication use.
- Urine specimen collection for urine human chorionic gonadotropin (HCG) (for pregnancy in women of child bearing potential).
- Blood collection for complete blood count (CBC) and Chemistry 15 panel.

#### Visit 1 (13 hours, fasting for at least 8 hours)

To start the study, eligible subjects will arrive at the clinic in the morning following an overnight fast (except for water) that began no later than 8 hours prior to the study appointment. The following tests and measurements will be performed:

- Weight, vital signs (blood pressure, pulse, and temperature).
- Blood collection for a CBC and Chemistry 15 panel.

- Subjects will be given a 150 mg dose of naringenin or placebo, administered orally.
- Blood collection for pharmacokinetic study of 150 mg dose of naringenin at 2, 3, 3.5, 4, 4.5, 6, 8, and 12 hours.
- Subjects will be provided a meal 5 hours after naringenin administration and at the end of the pharmacokinetic testing.

**Visit 1b (½ hour, fasting for at least 8 hours)**

- Subjects will return 24 hours post naringenin administration and blood will be drawn for CBC, Chemistry 15 panel, and to evaluate serum naringenin concentrations.
- Adverse events will be assessed 24 hours after naringenin dosing.

Subjects will return to the clinic to complete Visit 2 no less than seven days after the completion of Visit 1.

**Visit 2a (½ hour, fasting for at least 8 hours)**

Subjects will arrive at the clinic in the morning following an overnight fast (except for water) that began no later than 8 hours prior to the study appointment. The following tests and measurements will be performed:

- Weight and vital signs (blood pressure, pulse, and temperature).
- Blood collection for a CBC and Chemistry 15 panel.
- Subjects will consume 150 mg or 300 mg dose of naringenin or placebo, administered orally.

**Visit 2b (½ hour, fasting for at least 8 hours)**

- Subjects will return 24 hours post naringenin administration and blood will be collected for CBC, and Chemistry 15 panel.
- Adverse events will be assessed 24 hours after naringenin dosing.

Subjects will return to the clinic to complete Visit 3 no less than seven days after the completion of Visit 2.

**Visit 3a (5 hours, fasting for at least 8 hours)**

Subjects will arrive at the clinic in the morning following an overnight fast (except for water) that began no later than 8 hours prior to the study appointment. The following tests and measurements will be performed:

- Weight and vital signs (blood pressure, pulse, and temperature).
- Blood collection for a CBC and Chemistry 15 panel
- Subjects will consume 300 mg dose of naringenin or placebo, administered orally.
- Blood collection at four hours for measurement of serum naringenin.

**Visit 3b (½ hour, fasting for at least 8 hours)**

- Subjects will return 24 hours post naringenin administration and blood will be collected for CBC, Chemistry 15 panel, and serum naringenin concentrations.
- Adverse events will be assessed 24 hours after naringenin dosing.

The visits for Cohort 2 will be similar to Cohort 1 with the exception of oral naringenin dose to be administered (Table 1), and that BUN, AST, and Bilirubin will be added to the Chemistry 15 panel at visits 1a, 1b, 2a, 2b, 3a, and 3b.

## STUDY PROCEDURES

### Clinical Chemistry

**Safety Assessments:** Blood will be drawn at time 0 (before ingestion of each dose of naringenin, or placebo) and the subject will return 24 hours later (the next morning) for a repeat chemistry panel and CBC to assess safety of naringenin. Four ml of blood will be drawn for each of these tests. An additional 2 ml will be drawn with the 24 hour specimen to measure serum naringenin concentrations.

- Chemistry 15 Panel will be performed according to standard procedures for blood draws and the relevant chemistry panel.
- Comprehensive Blood Count (CBC) will be performed according to standard procedures.

**Pharmacokinetic Testing:** To evaluate the pharmacokinetics of naringenin, blood (two ml) will be drawn prior to administration of naringenin and at 2, 3, 3.5, 4, 4.5, 6, 8, 12 and 24 hours post-dose of 150 and 600 mg naringenin, and at four hours after the 300 and 900 mg doses. The serum will be separated from the blood, frozen and sent on dry ice to University of Tennessee for measurement of serum naringenin concentrations. This time course stretches over what is estimated to be five half-lives so a complete pharmacokinetic profile can be described including the maximal concentration achieved, time to peak, half-life, area under the curve, and apparent oral clearance ( $C_{max}$ ,  $T_{max}$ ,  $T_{1/2}$ ,  $AUC_{0-24hr}$  and  $Clearance_{oral}$  respectively).

### Adverse Events

An Adverse Event (AE) is defined as any untoward medical occurrence in a patient or clinical investigation subject, temporally associated with the use of a medicinal product, whether or not considered related to the medicinal product. We define AE as any unfavorable and unintended sign (including a clinically significant abnormal laboratory finding), symptom, or disease (new or exacerbated) temporally associated with the use of a medicinal product.

We will define a serious adverse event (SAE) as any untoward medical occurrence that results in death, is life threatening, requires inpatient hospitalization or prolongation of existing hospitalization, results in persistent or significant disability/incapacity or in a congenital anomaly.

Safety will also be assessed by recording all adverse events. The study team including coordinator and investigators will inquire regarding adverse events while minimizing the chance for bias when detecting AEs/SAEs. The study team will employ open-ended and non-leading verbal questioning of the subject as the preferred method to inquire about AE occurrence. For examples, appropriate questions include: "How are you feeling?", "Have you had any (other) medical problems since your last visit/contact?", or "Have you taken any new medicines, other than those provided in this study, since your last visit/contact?"

It is the responsibility of the investigator to attempt to establish a diagnosis of the event based on signs, symptoms, and/or other clinical information. In such cases, the diagnosis will be documented as the AE/SAE and not the individual signs/symptoms.

### ***Assessment of Causality***

The investigator is obligated to assess the relationship between study treatment and the occurrence of each AE/SAE. A "reasonable possibility" is meant to convey that there are facts/evidence or arguments to suggest a causal relationship, rather than a relationship cannot be ruled out. The investigator will use clinical judgment to determine the relationship. Alternative causes, such as concomitant therapy, other risk factors, and the temporal relationship of the event to the study treatment will be considered and investigated.

### ***Events meeting the definition of an AE:***

- Any abnormal laboratory test results (clinical chemistry) or other safety assessments (e.g., vital signs measurements), including those that worsen from baseline, and felt to be clinically significant in the medical and scientific judgment of the investigator.
- Exacerbation of a chronic or intermittent pre-existing condition including either an increase in frequency and/or intensity of the condition.
- New conditions detected or diagnosed after study treatment administration even though it may have been present prior to the start of the study.
- Signs, symptoms, or the clinical sequelae of a suspected interaction.
- Signs, symptoms, or the clinical sequelae of a suspected overdose of either study treatment or a concomitant medication (overdose per se will not be reported as an AE/SAE).

### ***Events that do not meet the definition of an AE:***

- Any clinically significant abnormal laboratory findings or other abnormal safety assessments that are associated with the underlying disease, unless judged by the investigator to be more severe than expected for the subject's condition.
- Medical or surgical procedure (e.g., endoscopy, appendectomy); the condition that leads to the procedure is an AE.
- Situations where an untoward medical occurrence did not occur (social and/or convenience admission to a hospital).
- Anticipated day-to-day fluctuations of pre-existing disease(s) or condition(s) present or detected at the start of the study that do not worsen.

### ***Reporting Procedures***

The reporting of SAE's will follow the standards of practice as outlined by the PBRC IRB in the investigator's responsibility policy (pages 4 and 5). Once the investigator determines that an event meets the protocol definition of an SAE, the SAE will be reported to the IRB within 24 hours. If the investigator does not have all information regarding an SAE, the investigator will not wait to receive additional information before notifying the responsible parties of the event and completing the appropriate forms. An assessment of causality at the time of the initial report will be provided. Email transmission of the SAE data collection tool will be the preferred method to transmit this information followed by notification by telephone and/or fax. A copy of the SAE report will also be sent to the institution officials. New or updated information will be recorded in the originally completed data collection tool. The investigator will submit any updated SAE data within 24 hours.

